**Secondary Endpoints**

- Rate of cardiac death or myocardial infarction (SCAI definition) from 1 to 13 months post-index procedure in the overall enrolled “intent-to-treat” patient population
- Rate of Academic Research Consortium (ARC) definite/probable stent thrombosis (ST) involving SYNERGY™Stents from 1 to 13 months post-index procedure
- Rate of major bleeding (GUSTO severe/life threatening + moderate) from 1 to 13 months post-index procedure
- Ischemia-Driven (ID) Target Lesion Revascularization,
- ID Target Vessel Revascularization,
- Target Lesion Failure,
- Target Vessel Failure,
- All-Cause Death, and
- All-Cause Death or MI.

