#### 6.4 STUDY INTERVENTION COMPLIANCE

Compliance to DAPT regimen will be ascertained at the 1-month follow-up visit and will be used to determine if the subject is eligible for discontinuation of P2Y12 inhibitor. During the 1-month follow-up visit, the subject will also be asked about any significant interruptions (greater than 3 days) in the prescribed index procedure.

Follow up at 30 days post DAPT cessation either by phone or clinic visit to assess angina status and targeted endpoints.

Note: All enrolled subjects who receive a SYNERGY™ Stents must be followed at all milestones through 13-months, regardless of eligibility to discontinue DAPT.

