### 7 STUDY INTERVENTION DISCONTINUATION AND PARTICIPANT DISCONTINUATION/WITHDRAWAL

#### 7.1 DISCONTINUATION OF STUDY PARTICIPATION

Subjects should not discontinue P2Y12 inhibitor (the patient will remain in the study until 13 months unless consent to participate is withdrawn) at 1 month if any of the following criteria are met:

- Subject experiences a stroke, MI, PCI, CABG and/or stent thrombosis, during the 1 month period following the index procedure
- Subject is non-compliant with DAPT regimen during the 1 month period following the index procedure. Non-compliant is defined as: DAPT interruption for at least 3 days.
- Subject judged to have another condition rendering them inappropriate for discontinuation from P2Y12 inhibitor at 1 month.

An investigator may discontinue or withdraw a participant from the study if:

- Pregnancy occurs
- Significant study non-compliance beyond DAPT compliance issues

- Continued participation in the study would not be in the best interest of the participant due to other conditions
- The participant is unwilling or unable to discontinue DAPT within 7 days after 30-day post-procedure visit
- Other unforeseen reason

Additionally, participants may withdraw from participation in the study at any time upon their own discretion and a request to the site.

The reason for participant discontinuation or withdrawal from the study will be recorded on Case Report Form (CRF). Subjects who sign the informed consent form but screen fail due to inclusion or exclusion criteria requirements will be replaced.

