## 8 STUDY ASSESSMENTS AND PROCEDURES

### 8.1 ADVERSE EVENTS AND SERIOUS ADVERSE EVENTS

#### 8.1.1 DEFINITION OF ADVERSE EVENTS (AE)

Adverse event means any untoward medical occurrence associated with the use of an intervention in humans, whether or not considered intervention-related (21 CFR 312.32 (a)).

All serious adverse events (SAE), adverse device effects (ADE), death, MI, stent thrombosis, as well as bleeding events will be collected from the start of the index procedure (sheath insertion) through the 13-month follow-up visit.

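### Section 7.1 allows a stented subject who does not stop DAPT to be withdrawn from the study, while section 6.4 requires that subject to be followed to 13 months

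*Combined protocol and SAP*

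**What the plan says.** Three statements govern what happens to a stented subject who does not stop DAPT at one month.

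- **Section 6.4 (compliance), closing note:** "All enrolled subjects who receive a SYNERGY™ Stents must be followed at all milestones through 13-months, regardless of eligibility to discontinue DAPT".
- **Section 7.1, first list:** this names subjects who should not stop the P2Y12 inhibitor at one month. One criterion is "Subject experiences a stroke, MI, PCI, CABG and/or stent thrombosis, during the 1 month period following the index procedure"; the others are non-compliance with DAPT and another condition that makes stopping inappropriate. For these subjects the section adds that "the patient will remain in the study until 13 months unless consent to participate is withdrawn".
- **Section 7.1, second list:** this opens with "An investigator may discontinue or withdraw a participant from the study if" and includes the bullet "The participant is unwilling or unable to discontinue DAPT within 7 days after 30-day post-procedure visit".

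Other sections bear on the consequence. Section 8.1.1 says that serious adverse events, death, MI, stent thrombosis and bleeding "will be collected from the start of the index procedure (sheath insertion) through the 13-month follow-up visit". Section 8.1.4 extends recording of serious adverse events to 30 days after a subject's last day of participation. The synopsis and section 3 define a secondary cardiac death/MI endpoint "from 1 to 13 months post-index procedure in the overall enrolled “intent-to-treat” patient population"; the primary endpoint uses subjects eligible for cessation at 30 days. Section 9.3 names an ITT dataset of all participants but leaves out those lost to follow-up. Section 9.2 replaces subjects lost to follow-up, and section 9.4.2 drops missing data and nonadherence from the final analysis.

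**The concern.** Leaving the DAPT-cessation strategy and leaving follow-up are different events, and the disputed bullet merges them. It permits removal from the study because of what the subject does about DAPT. Nothing in section 7.1 limits the bullet to the strategy, and nothing provides for the remaining endpoint contacts after withdrawal.

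This is a single-arm safety study, so no control group would suffer the same loss. If withdrawal depends on DAPT status, and if that status is related to prognosis, the rates in subjects still followed differ from those in all subjects treated. Because withdrawal is optional, sites may also handle identical subjects differently. Data lost this way may not be recoverable at analysis.

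**Working it through.** **1. The rules applied to each kind of stented subject who stays on DAPT**

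| Subject | Section 6.4 | Section 7.1, first list | Section 7.1, disputed bullet |
|---|---|---|---|
| Told not to stop P2Y12 (month-1 event, non-compliance, other condition) | Follow to 13 months | Stays in the study unless consent is withdrawn | May be withdrawn, if being told not to stop counts as being unable |
| Eligible to stop, but unwilling or otherwise does not | Follow to 13 months | Not covered | May be withdrawn |

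In the first row the bullet conflicts with section 6.4 and with section 7.1 itself, but only on the wider reading of unable. In the second row section 7.1 is consistent with itself, and the conflict with section 6.4 remains. No reading of the bullet agrees with section 6.4.

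**2. What is still collected after withdrawal**

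For a visit on day 30 and withdrawal at the end of the 7-day allowance, the last day of participation is 30 + 7 = day 37. Recording of serious adverse events then runs to 37 + 30 = day 67. The 7-month and 13-month contacts fall later and would be lost.

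**3. The plan's own figures (section 9.2)**

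Inputs: p0 = 0.031, p1 = 0.0047, one-sided alpha 0.05, power 0.95.

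- Arcsine formula: h = 2·asin(√0.031) − 2·asin(√0.0047) = 0.3540 − 0.1372 = 0.2168.
- n = ((1.645 + 1.645)/h)² = 230.3, rounded up to 231. The planned size is reproduced.
- Events implied by the plan's assumption: 231 × 0.0047 = 1.09.

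**4. What one event is worth**

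For the exact binomial test with n = 231 against 0.031:

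- P(X ≤ 2) = 0.025, below 0.05.
- P(X ≤ 3) = 0.071, above 0.05.

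The result turns on the difference between 2 and 3 events. This takes 3.1% as the reference and applies no Bonferroni adjustment. Section 9.2 gives that reference for the primary endpoint; the plan states no separate one for the ITT endpoint.

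**5. Illustration of the possible bias in the all-enrolled rate**

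The documents give neither the share withdrawn under this bullet nor those subjects' event rate. Assumptions: 5% to 15% of 231 are withdrawn (12 to 35 subjects); their 1-to-13-month rate lies between 3.1% (the plan's reference) and 8.8% (the top of its historical MI range, which covers MI only); everyone else has 0.47%; none of the withdrawn subjects' events is captured.

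- Low: (219 × 0.0047 + 12 × 0.031)/231 = (1.029 + 0.372)/231 = 0.61%.
- High: (196 × 0.0047 + 35 × 0.088)/231 = (0.921 + 3.080)/231 = 1.73%.
- Expected rate among those still followed: 0.47% in both cases.

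Under these assumptions the all-enrolled rate would look 0.14 to 1.26 percentage points too low. If the withdrawn subjects' rate were also 0.47%, there would be no bias.

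**The case against.** The best defence is that the two lists in section 7.1 serve different people. The first has its own retention rule, so the disputed bullet can be read as covering only subjects cleared to stop who do not. On that reading section 7.1 is coherent, and subjects with a month-1 MI, stroke or stent thrombosis are expressly kept. This stands as a reading of section 7.1. It does not remove the conflict with section 6.4, which covers every enrolled subject who receives the stent.

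Two further points stand in part. Withdrawal is a permission, so loss is possible and not certain. Serious adverse events are still recorded for 30 days afterwards, so collection does not end on the day of withdrawal.

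A reader might infer three stronger things that the documents do not support:

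- **That the highest-risk subjects are removed and the results are therefore biased toward safety.** This needs the wider reading of unable. Nothing shows that eligible but unwilling subjects are at higher risk.
- **That the other withdrawal grounds (pregnancy, best interest, study non-compliance, unforeseen reasons) contradict section 6.4 in the same way.** The note in 6.4 is framed around eligibility to stop DAPT, and those grounds can be read as ordinary exceptions. The pregnancy reporting in section 8.1.9 does not require the subject to stay in the study.
- **That the primary endpoint is clearly compromised.** Its population is limited to subjects eligible for cessation, so those told not to stop are outside it by design. It is touched only if eligible but unwilling subjects are removed, and an as-treated set might leave them out anyway.

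**Conclusion.** The point holds as an internal contradiction in the current text with a real consequence for the data. Section 7.1 permits an exit from the study that section 6.4 does not allow, and on the wider reading of unable it also contradicts its own retention sentence.

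The main exposure is the ITT cardiac death/MI endpoint and the death, stent thrombosis and bleeding rates in all enrolled subjects. An effect on the primary endpoint is possible but secondary. The direction of any bias depends on whether the subjects withdrawn have a worse prognosis, which is plausible for some of them and not shown for others.

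The size cannot be derived from the documents. The 0.14 to 1.26 percentage points above rest on assumed withdrawal shares and event rates. The firmer statement is that about 1.09 events are implied in 231 subjects, so one uncollected event is material.

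**What to change.** Reconcile sections 6.4 and 7.1:

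- Remove the bullet on not discontinuing DAPT as a ground for leaving study follow-up.
- State that not stopping DAPT does not end follow-up, and that these stented subjects are followed for all endpoints through 13 months unless they withdraw consent.
- Record the reason for not stopping and the P2Y12 status.
- In section 9.4.2, state that the nonadherence exclusion does not drop these subjects from the ITT analysis. Without this, data secured by the first change could still be discarded.

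Leave the other withdrawal grounds and every rule on who stops P2Y12 as they are. The sample size stays at 231.

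The cost is protocol wording, one CRF field, a few contacts that the schedule already contains, and possibly a slightly less favourable ITT rate.

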## 7.2 LOST TO FOLLOW-UP

A participant will be considered lost to follow-up if he or she fails to return for any of the study follow-up visits and/or is unable to be contacted by the study site staff.

The following actions must be taken if a participant fails to return to the clinic for a required study visit:

- The site will attempt to contact the participant and reschedule the missed visit and counsel the participant on the importance of maintaining the assigned visit schedule and ascertain if the participant wishes to and/or should continue in the study.
- Before a participant is deemed lost to follow-up, the investigator or designee will make every effort to regain contact with the participant (where possible, 3 telephone calls and, if necessary, a certified letter to the participant's last known mailing address or local equivalent methods). These contact attempts should be documented in the participant's medical record or study file.
- Should the participant continue to be unreachable, he or she will be considered to have withdrawn from the study with a primary reason of lost to follow-up.

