**Specific Definitions of Adverse Events:****DEATH**

All deaths are considered cardiac unless a non-cardiac cause can be documented.

- Cardiac death: Any death due to immediate cardiac cause (e.g. MI, low-output failure, fatal arrhythmia). Unwitnessed death and death of unknown cause will be classified as cardiac death.
- Non-cardiac death: Any death not covered by the above definition, including death due to pulmonary causes, accident, suicide, infection, sepsis, or trauma.

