## 9.2 THE ALTERNATIVE HYPOTHESIS STATES THAT PATIENTS UNDERGOING SYNIVUS-DAPT TREATMENT WILL HAVE LOWER RATES OF MYOCARDIAL INFARCTION OR CARDIAC DEATH. SAMPLE SIZE DETERMINATION

An a priori power analysis was conducted for a one-sample binomial test with an alpha of .05 (one-tailed), beta of .05, constant proportion ( $p$ ) of .031, and assumed primary endpoint proportion of 0.0047 resulting in a needed sample size of 231.

The consideration of historical data on timing and incidence of myocardial infarction and stent thrombosis from published meta-analysis and related literature, the SCAAR registry and ACS subsets (De Luca, Dirksen, Spaulding, et al, 2012; Ellis, Colombo, Grube, et al, 2007; Palmerini, Biondi-Zocca, Riva, et al, 2012; Palmerini, Kirtane, Serruys, et al, 2012; SCAAR registry and ACS subset, 2016). Historic rates at 1-year follow up for ST showed variability ranging from 0.3 to 5.3%. Rates of MI range from 1.9 to 8.8%. A time-to-event bivariate exponential distribution function was used to determine criteria for sample sizes based on a 95% power determination resulting in a historic rate determination of 3.1%. Patients lost to follow-up will not be included in the final analysis, and additional patients will be recruited for study participation to reach the needed sample of 231.

The FDA has approved an initial phase of the investigation for 100 U.S patients. Accordingly, the sample size of N=100 for the initial phase is not statically based. Should approvals for study continuation be granted, the total sample size for subsequent phases will remain at 231, inclusive of subjects enrolled on this initial phase.

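### Section 7.2 records an unreachable patient as withdrawn without a vital-status check, a retry at later milestones or reinstatement, so a death the site never learns of leaves the primary endpoint

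*Combined protocol and SAP*

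**What the plan says.** Section 7.2 opens: "A participant will be considered lost to follow-up if he or she fails to return for any of the study follow-up visits" and/or cannot be contacted by site staff. Its bullets describe a longer process. After a missed visit, "The site will attempt to contact the participant and reschedule the missed visit". Before the lost label is applied, the site must make every effort to regain contact: three telephone calls where possible and, if necessary, a certified letter or a local equivalent. If the patient still cannot be reached, "he or she will be considered to have withdrawn from the study with a primary reason of lost to follow-up".

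Four other parts of the plan bear on this:

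- **Section 6.4:** all enrolled patients who receive the study stent "must be followed at all milestones through 13-months, regardless of eligibility to discontinue DAPT".
- **Section 8.1.1:** deaths are collected from sheath insertion to the 13-month visit and are cardiac unless a non-cardiac cause is documented. "Unwitnessed death and death of unknown cause will be classified as cardiac death".
- **Section 1.3:** the 60-day, 7-month and 13-month contacts may be made in the office or by phone.
- **Sections 9.2, 9.3 and 9.4.2:** patients lost to follow-up are left out of the analysis. Section 9.2 adds that further patients are recruited to reach 231.

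**The concern.** The opening sentence of 7.2 can be read as assigning lost status after one missed visit. The bullets do not support that reading, and 6.4 points the other way, so sites could apply the rule differently. The wording about failing to return also does not fit contacts that may be made by phone.

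The larger problem is what happens once the attempts fail. They are aimed only at the participant. The plan does not call for a check of vital status, an approach to an alternate contact or treating physician, another try at the next milestone, or re-entry of a patient who is found later. A patient who misses the 60-day contact and does not answer can be closed out with two scheduled contacts still to come.

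The death rule in 8.1.1 is conservative, but it works only if the site learns of the death. A patient who died unwitnessed at home cannot answer a call or a letter. Under 7.2 that patient can end as a withdrawal, and section 9 then removes and replaces the patient. A missed death can only lower the observed rate of cardiac death or MI, which favours a finding of safety. Changing the analysis rules alone would not recover a death that nobody looked for.

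**Working it through.** **Inputs.** Section 9.2 gives a "one-sample binomial test with an alpha of .05 (one-tailed), beta of .05", a constant proportion "of .031, and assumed primary endpoint proportion of 0.0047", "resulting in a needed sample size of 231". So p0 = .031, p1 = .0047, one-sided alpha = .05 and power = .95. The documents give no loss rate. I assume 2%, 5% and 10%.

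**Step 1: the plan's sample size.** With the arcsine formula, n = ((z_alpha + z_beta)/h)², where h = 2·arcsin(√p0) − 2·arcsin(√p1).

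- h = 0.3540 − 0.1372 = 0.2168
- n = ((1.645 + 1.645)/0.2168)² = 230.3, so 231

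The stated figure reproduces.

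**Step 2: the success limit at 231.** Exact one-sided p = P(X ≤ k) for X ~ Binomial(231, .031).

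| Events k | Exact p |
|---|---|
| 1 | .006 |
| 2 | .025 |
| 3 | .071 |

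The limit is 2 events, at .05 and also at the final-analysis level of .0492 in section 9.4.4.

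**Step 3: patients enrolled to obtain 231 evaluable.** N = 231/(1 − d), rounded up, for loss rate d.

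- d = 2%: 231/0.98 = 235.7, so 236 enrolled and 5 lost
- d = 5%: 231/0.95 = 243.2, so 244 enrolled and 13 lost
- d = 10%: 231/0.90 = 256.7, so 257 enrolled and 26 lost

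**Step 4: missed deaths at the limit.** The analysed 231 show 2 events, p = .025. Now restore the lost patients to the denominator and add the missed cardiac deaths: p = P(X ≤ 2 + m) for X ~ Binomial(N, .031).

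| Assumed loss | N | m = 1 | m = 2 |
|---|---|---|---|
| 2% | 236 | .064 | .142 |
| 5% | 244 | .054 | .124 |
| 10% | 257 | .041 | .098 |

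One missed death reverses the result at 2% or 5% loss. At 10% loss it takes two.

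**Step 5: chance of a false success.** Suppose the true overall rate is 3.1% and the event rate among lost patients is q. The rate among retained patients is r = (.031 − d·q)/(1 − d), and the chance of a false success is P(X ≤ 2) for X ~ Binomial(231, r). With no informative loss it is .025.

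| Assumed loss | q = 10% | q = 20% |
|---|---|---|
| 2% | .032 | .046 |
| 5% | .047 | .113 |
| 10% | .093 | .463 |

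For example, at d = 5% and q = 10%, r = (.031 − .005)/.95 = .0274. Both d and q are assumptions. The table shows direction and range and is not a forecast.

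**The case against.** The strongest reply is that 7.2, read whole, is more careful than its first sentence. A missed visit leads to rescheduling, and the label follows only after documented attempts fail. That stands. A reader might infer that one missed visit removes a patient, and the bullets do not support this.

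A reader might also infer that 7.2 turns deaths of unknown cause into withdrawals. It does not. Section 8.1.1 collects and classifies every death the site knows of, and section 8.1.4 lets events come to light when a patient presents for care or through monitor review. The gap is limited to deaths that nobody learns of and to patients found after the attempts have failed.

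Section 7.2 holds no analysis rule. Removal from the endpoint comes from section 9, triggered by the status that 7.2 assigns.

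The arithmetic is a boundary case. Exactly 3 events in 231 has probability 7.2% at a rate of .0047 and 4.6% at .031. It would be too strong to say that one missed death turns failure into success in general; at 10% loss it does not. No figure in the documents shows that silent patients are more likely to have died. That is a reasonable inference in a high-bleeding-risk population, but age 75 or over is only one of nine alternative entry criteria. The manual of procedures mentioned in 10.1.10 and the CRF are not available here and may already cover part of this.

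**Conclusion.** The concern holds in this limited form. The opening sentence of 7.2 conflicts with its bullets and with 6.4. More importantly, the plan lets an unreachable patient be closed out with no vital-status check, no later retry and no way back. Together with the exclusions and replacement in section 9, a death that is never ascertained is lost to the primary endpoint, and the error runs towards safety.

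With a limit of 2 events, one such death is enough to reverse a just-significant result at 2% or 5% loss, and two are enough at 10%. This rests on the assumed loss rates, on a result at the limit, and on the missed death being one that 8.1.1 would class as cardiac within the 1 to 13 month window. The change should be made: it is cheap and protects a safety endpoint decided by very few events.

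**What to change.** Reword 7.2 as follows.

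1. A missed contact is a missed visit only. Contact is tried again at each later milestone (60 days, 7 months, 13 months).
2. Lost status is assigned only when the 13-month window closes. It follows a documented check of vital status and admissions through medical records, an alternate contact or treating physician, and public death records, as consent permits.
3. A patient found later is reinstated, and any death found is classified under 8.1.1.
4. Lost to follow-up is recorded separately from withdrawal of consent and from investigator withdrawal under 7.1, whose grounds stay as they are.

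The cost is a few record checks by existing coordinators, protocol wording, CRF fields for vital status and an alternate contact if they are not already there, and possibly consent wording.

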## 8 STUDY ASSESSMENTS AND PROCEDURES

### 8.1 ADVERSE EVENTS AND SERIOUS ADVERSE EVENTS

#### 8.1.1 DEFINITION OF ADVERSE EVENTS (AE)

Adverse event means any untoward medical occurrence associated with the use of an intervention in humans, whether or not considered intervention-related (21 CFR 312.32 (a)).

All serious adverse events (SAE), adverse device effects (ADE), death, MI, stent thrombosis, as well as bleeding events will be collected from the start of the index procedure (sheath insertion) through the 13-month follow-up visit.

